### **Study Duration:**

The duration of the clinical phase is approximately 10 weeks for each subject. This includes a screening period of up to 2 weeks, a treatment period of 8 weeks, and a final exit visit at Week 8 (Day 56).

### 5.3.1 Study Design

The overall study design is shown in Figure 1. The schedule of assessments for individuals is shown in Table 1.

# Figure 1 Overall Study Design

Oxy Cream - Oxymetazoline HCl Cream 1.0% once daily

Energy-Based Therapy - Potassium Titanyl Phosphate (KTP), Pulsed Dye Laser (PDL) or Intense Pulsed Light (IPL) Therapy

Allergan

CMO-MA-MED-0530

# 06 Feb 2018

Version 2

Page 18 of 59

Study Period	Screening*	Day 1/ Baseline*	Day 3	Day 29	Day 31	Day 56/ Exit Visit
Visit Window	Day -14 to Day -1	N/A	N/A	± 3 Days	+2 days from Day 29	± 3 Days
Informed Consent	Х					
Demographics	Х					
Fitzpatrick Skin Phototype	Х					
Inclusion/Exclusion Criteria	Х	X a				
Medical History	Х	X b				
Physical Examination	Х					Х
Vital Sign Measurement	Х	X a	Xc	X a	X c	Х
Urine Pregnancy Test (if applicable)	Х	X a,b				Х
Energy-Based Therapy (KTP, PDL, or IPL)		Х		Х		
Onsite Study Drug Treatment/Dispensing			Х		Х	X d
Standardized Photography		X e	X f	X e	X f	X f
Clinician Erythema Assessment (CEA)		X e	$\mathbf{X}^{\mathbf{f}}$	X e	Xf	X f
Clinician's Telangiectasia Assessment (CTA)	X	X a,b	X a	X a	X a	X a
Items From Satisfaction Assessment for Rosacea Facial Redness	Х	X a,b	X g		X g	X g
FACE-Q Satisfaction With Skin Scale	Х	X a,b		X a		X a
Dermal Tolerability Assessment (Investigator and Subject)		X e	$X^h$	X e	X h	X h
Adverse Events/Reactions	۹					
Concomitant Medications and Concurrent Procedures	◀					

### Table 1 Schedule of Assessments and Procedures

\* Screening and baseline may occur on same day

a predose (Oxymetazoline HCl)/pretreatment (Energy-based therapy [KTP, PDL, or IPL])

b repeated only if screening/Day1 occur on separate days

c predose/pretreatment and 6 hr

d Study drug application only. No study drug will be dispensed

e predose/pretreatment and 1 hr

fpredose, 1 hr, 3 hr, and 6 hr

g 6 hr

h predose/pretreatment 1 hr and 6 hr

#### Acceptable Time Window Deviations

Predose – all predose assessments on Day 1 and Day 29 should occur within 90 minutes prior to energy-based treatment. All predose assessments on Day 3, Day 31, and Day 56 should occur within 90 minutes prior to study drug administration.

Postdose – all assessments performed at the 1 hour, 3 hour, and 6 hour postdose timepoints should be performed within 15 minutes (ie, 1 h ±15min, 3 h±15min, 6 h ±15min).

CONFIDENTIAL

# 5.4 Discussion of Study Design

The study will take place in subjects with moderate to severe persistent facial erythema of rosacea in order to ascertain whether once-daily application of oxymetazoline HCl 1.0% cream is safe and well tolerated when used as an adjunct to energy-based therapies known to improve erythema and telangiectasia in rosacea subjects. For further details on study drug and energy-based therapy dose and treatment design refer to Section 5.6.

# 5.5 Selection of Study Population

# 5.5.1 Number of Planned Subjects

The total planned number of subjects is 45.

# 5.5.2 Inclusion Criteria

To be eligible for study entry, subjects must satisfy all of the following inclusion criteria:

- 1. Subject has provided written consent prior to any study-related procedures.
- 2. Male or female aged  $\geq$  18 years.
- 3. Documented clinical diagnosis of rosacea.
- 4. Moderate to severe persistent facial erythema associated with rosacea at baseline, as determined by a grade of  $\geq$  3 on the CEA scale with photonumeric guide.
- 5. Females of childbearing potential must not be lactating, must have a negative urine pregnancy test at screening and Day 1, and must agree to practice a reliable method of contraception throughout the study (see Section 5.6.9).
- 6. The ability to follow study instructions and complete study assessments without assistance and have a willingness and ability to comply with all scheduled visits, treatment plan, and other study procedures.

# 5.5.3 Exclusion Criteria

Subjects will be excluded from the study if 1 or more of the following criteria are applicable:

- 1. Any uncontrolled systemic disease.
- History of any of the following conditions: Raynaud's syndrome, narrow angle glaucoma, orthostatic hypotension, cerebral or coronary insufficiency, thromboangiitis obliterans, scleroderma, Sjögren's syndrome, severe or unstable or uncontrolled cardiovascular disease, or any other current uncontrolled systemic disease.
- 3. Diagnosis or presence of any of the following conditions within the treatment area: rosaceaconglobata, rosacea fulminans, isolated rhinophyma, isolated pustulosis of the chin, peri-oral dermatitis, demodicidosis, facial keratosis pilaris, seborrheic dermatitis, acute lupus erythematosus, or chronic recurring facial acne.
- 4. The presence of facial hair, tattoos, or other facial characteristics such as actinic damage (eg, actinic lentigines, mottled hyperpigmentation or hypopigmentation, yellowish

discoloration, excessive telangiectasia) that could interfere with the assessments of erythema in the opinion of the investigator.

- 5. Current treatment with monoamine oxidase (MAO) inhibitors.
- 6. Current treatment with niacin  $\geq$  500 mg/day.
- 7. Any of the following treatments occurring within the specified period prior to Day 1:
  - 14 days: products containing oxymetazoline (eg, eye drops, nasal sprays), topical glucocorticosteroids applied to the face, systemic or nasal corticosteroids, any prescription or over-the-counter (OTC) product for the treatment of acne.
  - 28 days: Systemic antibiotics that are known to have an effect on rosacea such as erythromycin or doxycycline.
  - 180 days: isotretinoin.
- 8. Prior dermal adverse reaction to using Mirvaso® (brimonidine) topical gel, 0.33% or current use of marketed Mirvaso® (brimonidine) topical gel, 0.33%.
- 9. Previous participation in clinical trials associated with oxymetazoline cream for facial rosacea
- 10.Known hypersensitivity or allergies to any component of the study drug.
- 11.Greater than 3 inflammatory lesions on the face.
- 12.Current enrollment in an investigational drug or device study or participation in such a study within 30 days of entry into this study.
- 13. History or current evidence of drug or alcohol abuse within 12 months prior to the screening visit.
- 14.Condition or situation that, in the investigator's opinion, may put the subject at significant risk, may confound the study results, or may interfere significantly with the subject's participation in the study.
- 15.An employee (or a relative of an employee) of the investigators, Allergan, or representative of Allergan.

### 5.5.4 Removal of Subjects From Therapy or Assessments

Subjects may stop study drug for any of the following reasons:

- · Subject request
- Use of non-permitted concurrent therapy
- Non-compliance with the study drug or study schedule
- Lost to follow-up
- Occurrence of AEs that are not compatible with the continuation of subject participation in the study, in the investigator's opinion, or are unacceptable to the subject to continue
- Investigator request
- Intercurrent illness
- Sponsor request
- Treatment failure

Allergan		06 Feb 2018
CMO-MA-MED-0530	Version 2	Page 21 of 59

### Pregnancy

Subjects who do not comply with the protocol, withdraw consent, or stop study drug for any other reason will not be replaced. Subjects are free to withdraw from the study at any time without providing reason(s) for withdrawal and without prejudice to further treatment. The reason(s) for withdrawal will be documented in the electronic case report form (eCRF).

Upon withdrawal from the study, any time after dosing has taken place, all efforts should be made to invite the subject to complete the early withdrawal visit. The same procedures should be performed as on the Day 56 (exit visit). The aim is to record data in the same way as for subjects who completed the study, particularly safety data.

Reasonable efforts will be made to contact subjects who are lost to follow-up. These efforts should be documented in the subject's file.

The sponsor has the right to terminate the study at any time in case of SAEs or if special circumstances concerning the study drug/energy therapy or the company itself occur, making further treatment of subjects impossible. In this event, the investigators will be informed of the reason for study termination.

# Pregnancy

Subjects will be instructed that known or suspected pregnancy occurring during the study, in subjects or female partners of male subjects, should be confirmed and reported to the investigator, who will then withdraw the female subject from the study without delay. Upon discontinuation from the study, only those procedures that would not expose the subject to undue risk will be performed. The investigator should also be notified of pregnancy occurring during the study but confirmed after completion of the study. In the event that a subject is subsequently found to be pregnant after inclusion in the study, any pregnancy will be followed to term, and the status of mother and child will be reported to the sponsor after delivery.

Full details will be recorded on the withdrawal page of the eCRF, and a Pregnancy Data Form should be completed and faxed/emailed to Allergan within 24 hours of awareness of the event using the contact details in Section 7.1.2.1.1.

# 5.6 Investigational Products and Therapies

# 5.6.1 Investigational Products Administered

Oxymetazoline HCl cream 1.0% will be applied in a thin layer topically to the entire face including forehead, nose, each cheek, and chin, once daily. Subjects will be instructed to apply study drug to their clean, dry face in the morning, at approximately the same time each day, starting on Day 3 through Day 56. There will be a 3 day washout period from the study drug beginning 24 hours prior to the second energy-based therapy session on Day 29 (subjects will not apply the study drug on Day 28, Day 29, and Day 30) to ensure that energy-based therapy and treatment with oxymetazoline are clearly separated in the case of any treatment-related adverse events. The Investigator should assess if any adverse events resulting from treatment with the energy-based device (eg, treatment site skin irritation or wounding) would present a risk for treatment with oxymetazoline and either delay or discontinue treatment.

For study visits, subjects will be instructed to apply the study drug at the study site. The dose will be applied after predose study assessments and procedures are completed. Site personnel

Allergan		06 Feb 2018
CMO-MA-MED-0530	Version 2	Page 22 of 59

will observe subject dosing in the clinic to ensure proper study drug application technique and retrain if necessary. Detailed instructions on study drug application will be provided to subjects (see Section 5.6.12).

# 5.6.2 Identity of Investigational Products

Oxymetazoline cream 1.0% (Rhofade) contains oxymetazoline HCl, methylparaben, propylparaben, phenoxyethanol, sodium citrate dihydrate, citric acid anhydrous, disodium edetate, butylated hydroxytoluene, anhydrous lanolin, medium chain triglycerides, diisopropyl adipate, oleyl alcohol, polyethylene glycol (PEG)-300, PEG-6 (and) PEG-32 (and) glycol stearate, cetostearyl alcohol, ceteareth-6 (and) stearyl alcohol, ceteareth-25, and purified water.

# 5.6.3 Packaging and Labelling

All study drug will be supplied by Allergan. The study drug will be packaged in identically appearing containers consistent with all applicable regulations. The medication will be supplied in the approved commercial packaging. The study drug container will have a child-resistant feature. Labelling on the container and the carton will include the following statements: "For Topical Use Only" and "Keep Out of Reach of Children."

# 5.6.4 Energy-Based Therapies

Subjects will receive one of the following 3 types of energy-based therapy at the timepoints indicated in Table 1 during the study:

**Pulsed Dye Laser (PDL):** The following 2 PDL devices will be utilized for this study: Cynergy (Cynosure) and Vbeam Perfecta (Syneron-Candela). The Pulsed Dye Laser (PDL) delivers pulsed laser energy at a wavelength that targets hemoglobin and results in the destruction of superficial blood vessels, reducing both erythema and telangiectasia.

**Potassium Titanyl Phosphate Laser (KTP):** The KTP utilized for this study will be the Excel V (Cutera). The KTP laser has been shown to improve telangiectasia to a greater extent than erythema in rosacea patients.

**Intense Pulsed Light Therapy (IPL):** The IPL utilized for this study will be the Palomar Icon (Cynosure). IPLs emit polychromatic light and are commonly used to treat vascular lesions associated with rosacea.

Each study center will be assigned one or more devices from the list above to utilize during the study. Each study center will utilize only the specific devices assigned for use at their site. The devices will be assigned based on the current expertise and devices present at the study center.

Approximately 11 subjects will be treated with each energy-based therapy device type. The method for treatment with laser at each site will be based on the Investigator's current standard of practice. The details of the study treatment (ie, wavelength, pulse duration, number of pulses, and fluence) will be recorded in the eCRF for each subject.

# 5.6.5 Methods of Assigning Subjects to Treatment Groups

Subjects who meet all inclusion/exclusion criteria will be assigned a subject enrolment number that will serve as the subject identification number on all study documents.

All eligible subjects will receive oxymetazoline HCl cream 1.0%.

Allergan		06 Feb 2018
CMO-MA-MED-0530	Version 2	Page 23 of 59

There is no stratification of randomization associated with this study. Subjects will be assigned to 1 of 3 types of energy-based therapy, based on the assigned devices at the site they attend. Enrolment at each study center will be monitored to ensure that a minimum of 11 subjects will receive each type of energy-based therapy.

# 5.6.6 Selection of Doses in the Study

Oxymetazoline HCl cream 1.0% applied once daily for treatment of persistent facial erythema of rosacea has been evaluated by Allergan in 3 Phase 3 studies, with duration of application extending from 29 days to 52 weeks. The results from these studies consistently demonstrated that oxymetazoline HCl cream 1.0% was safe and well tolerated based upon multiple safety evaluations, and demonstrated consistent trends in efficacy, with improvements from baseline observed throughout the treatment period.

# 5.6.7 Selection and Timing of Energy Therapy

Laser and light therapy have been shown to reduce erythema and telangiectasia in patients with rosacea. Subjects will be allocated to one of KTP, PDL, or IPL treatments and undergo 2 sessions (Day 1 and Day 29) during the study. The 28-day period between the 2 treatments is standard in current practice allowing for efficacious results.

Subjects will begin study drug administration on Day 3 (2 days after the first energy-based therapy session) and will washout study drug from 24 hours prior to the second energy-based therapy session on Day 29, until 2 days after (Day 31). This will ensure that the study drug will not be present on the skin during the energy-based therapy or during the immediate recovery period during which there may be irritation to the skin. Any post-treatment skin irritation will be identified by the physician during this washout period and oxymetazoline treatment will not recommence until deemed safe to do so.

# 5.6.8 Blinding

This study will be an open-label study, therefore blinding of the study drug or treatments is not required.

# 5.6.9 Contraceptive Requirements

Females of child bearing potential are defined as any female subject post-puberty. Females that are postmenopausal (defined as having 12 months of consecutive spontaneous amenorrhea) or surgically sterile (6 months post-surgical bilateral oophorectomy with or without hysterectomy, 6 months post-hysterectomy, or 6 months post-tubal ligation) are exempt from the contraceptive requirements of the study.

Females of childbearing potential are required to use effective contraception from the time of signing the ICF until the end of the study. Acceptable methods of contraception are intrauterine devices, hormonal contraceptives (eg, oral, patch, or injectable), partner's vasectomy (if this is the sole partner and vasectomy was medically confirmed), a double barrier protection method (eg, condom or diaphragm with spermicide cream, foam, or gel), or sexual abstinence. Periodic abstinence [calendar, ovulation, symptothermal, post ovulation methods] and withdrawal are not acceptable methods of contraception.

# 5.6.10 Prior and Concomitant Therapy

Therapy considered necessary for the subject's welfare may be given at the discretion of the investigator, including but not limited to medications for other conditions (ie, hypertension, diabetes, etc.), treatment of AEs, estrogens, androgens, anti-androgenic agents, vitamins, iron supplements, folate, and herbal supplements. Medications should be taken consistently throughout the study and at the investigator's discretion.

Concomitant medications as defined for this study include dietary supplements, OTC medications, and oral herbal preparations, as well as changes in dosages of current prescription medications. Concomitant medications will be documented for each subject at each scheduled visit. A detailed history of medications will be documented at screening. Subsequently, at each study visit, subjects will be asked what medication, if any, they have taken since the previous visit. All concomitant medications will be recorded in the eCRF.

# 5.6.10.1 Prohibited Medication/Therapy

The decision to administer a prohibited medication/treatment is done with the safety of the subject as the primary consideration. When possible, Allergan should be notified before the prohibited medication/treatment is administered.

The following products are prohibited under this study:

- 1. Products containing oxymetazoline, except for study drug.
- Any prescription, OTC, or herbal topical and/or systemic product that has a known effect on rosacea (eg, Mirvaso [brimonidine] topical gel, 0.33%, metronidazole-containing products, azelaic acid-containing products, systemic antibiotics such as erythromycin or doxycycline).
- 3. Any prescription, OTC, or herbal product applied to the face that causes vasoconstriction.
- 4. Any prescription, OTC, or herbal product that is primarily used to decrease facial redness.
- 5. Any topical facial treatment that may affect erythema or cause skin irritation.
- 6. New topical facial regimens.
- 7. Topical glucocorticosteroids applied to the face.
- 8. MAO inhibitors.
- 9. Isotretinoin.
- 10. Any new use of systemic or inhaled glucocorticosteroids, cardiac glycosides, alpha-1 adrenergic receptor antagonists,  $\beta$ -adrenergic blocking agents (topical or systemic),  $\beta$ -adrenergic agonists, antihypertensive agents, or  $\geq 500 \text{ mg/day}$  niacin.
- 11. Medications that the subject knows may increase their facial erythema or cause flushing.

#### 5.6.10.2 Prohibited Treatments

Laser, light-source, or other energy-based therapies to the face, other than those treatments performed as part of the study, are not permitted during the study.

Dermatological treatments on the face (eg, facial peels, microdermabrasion, exfoliating treatments) are prohibited for the duration of the study.

# 5.6.10.3 Prohibited Activities

Twenty-four hours before all study visits, the following activities are prohibited:

- 1. Consumption of any food, alcohol, or other beverage that the subject knows increases their facial erythema.
- 2. Use of saunas, steam rooms, and hot tubs, or any other activities that the subject knows will increase their facial erythema.

During all study visits, application of any facial products (eg, sunscreen, moisturizer, makeup) is prohibited from 2 hours before the first assessment until all assessments are complete. Facial cleansers are allowed; however, application of study drug and study assessments should occur at least 20 minutes after the cleanser is used.

# 5.6.10.4 Dietary Requirements at Site

Subjects will remain at the investigational site for at least 6.5 hours during the Day 3, Day 31, and Day 56 Visits. The study site will provide meals and beverages during these visits. Subjects may only consume the food and beverages provided by the study staff, unless they require a special diet that they bring from home, under study site supervision. The meals should not include items that may increase any of the subjects' facial erythema, such as certain spices, caffeine, nicotine, hot beverages, or alcohol. Subjects may consume water at their discretion.

# 5.6.11 Treatment Compliance

At each visit after Day 1 subjects will be asked if they have used any concomitant medications, had any concurrent procedures, used any prohibited medications/treatments, or participated in any prohibited activities since the previous visit. At each visit after Day 3 subjects will also be asked if they have applied the study drug every day in the morning. Any breach of compliance will be recorded in the eCRF.

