#### Treatment:

All subjects will receive one of the following energy-based therapies: Potassium Titanyl Phosphate [KTP], Pulsed Dye Laser [PDL], or Intense Pulsed Light [IPL] twice during the study (Day 1 and Day 29). Once-daily application of oxymetazoline HCl cream 1.0% will be initiated on Day 3 and continued until Day 56. Subjects will be washed out from study drug 24 hours prior to the energy-based therapy session on Day 29 and will recommence study drug administration on Day 31.

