# 6.1.2 Baseline Visit (Day 1)

The Day 1 Baseline Visit will take place up to 14 days after the Screening Visit. The screening and Day 1 baseline assessments may be performed on the same day. The following procedures will be performed at the Day 1 Baseline Visit (at the timepoints indicated in Table 1):

- Reconfirm inclusion/exclusion criteria.\*
- Record any AEs/TEAEs and changes in concomitant medication or concomitant procedures.
- Collect updated medical history.\*
- Vital sign measurement (blood pressure, pulse rate, oral body temperature).
- Urine pregnancy test (for women of childbearing potential only).\*
- CTA.
- Energy-Based Therapy (KTP, PDL, or IPL).
- Standardized photography of treatment area.
- CEA.
- Dermal Tolerability Assessment (investigator and subject).
- Items from Satisfaction Assessment for Rosacea Facial Redness.\*
- FACE-Q Satisfaction with Skin Scale.\*

\* only performed if screening and baseline assessments performed on separate visits.

# 6.1.3 Day 3

The subject will return to the site on Day 3 and the following procedures will be performed (at the timepoints indicated in Table 1):

- Record any AEs/TEAEs and changes in concomitant medication or concomitant procedures.
- Vital sign measurement (blood pressure, pulse rate, oral body temperature).
- CTA.
- Standardized photography of treatment area.
- CEA.
- Dermal Tolerability Assessment (investigator and subject).
- Items from Satisfaction Assessment for Rosacea Facial Redness.
- · Application and dispensing/collection of study drug.

The subject will be instructed how to apply the study drug at this visit and will be given a sufficient supply to enable once-daily application from Day 4 until Day 27. The subject will be instructed not to apply study drug on Day 28, Day 29, and Day 30.

#### 6.1.4 Day 29

The subject will return to the site on Day 29 and the following procedures will be performed (at the timepoints indicated in Table 1):

- Record any AEs/TEAEs and changes in concomitant medication or concomitant procedures.
- Vital sign measurement (blood pressure, pulse rate, oral body temperature).
- CTA.
- Standardized photography of treatment area.
- CEA.
- Dermal Tolerability Assessment (investigator and subject).
- Energy-Based Therapy (KTP, PDL, or IPL).
- FACE-Q Satisfaction with Skin Scale.

# 6.1.5 Day 31

The subject will return to the site on Day 31 and the following procedures will be performed (at the timepoints indicated in Table 1):

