- Record any AEs/TEAEs and changes in concomitant medication or concomitant procedures.
- Vital sign measurement (blood pressure, pulse rate, oral body temperature).
- CTA.
- Standardized photography of treatment area.
- CEA.
- Dermal Tolerability Assessment (investigator and subject).
- Items from Satisfaction Assessment for Rosacea Facial Redness.
- Application and dispensing/collection of study drug.

The subject will be given sufficient study drug to enable once-daily application from Day 32 to the Day 56 exit visit.

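### The cream break around the second energy session is set by fixed day numbers rather than by the session, and the compliance question neither fits the break nor checks it

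*Protocol*

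**What the plan says.** The washout rule is relative to the session. The synopsis (Treatment) states: "Subjects will be washed out from study drug 24 hours prior to the energy-based therapy session on Day 29". Protocol Section 5.6.7 has the break run until two days after the session. Section 5.6.1 gives one purpose of the break: "to ensure that energy-based therapy and treatment with oxymetazoline are clearly separated in the case of any treatment-related adverse events". Section 5.6.7 gives the other: "This will ensure that the study drug will not be present on the skin during the energy-based therapy".

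The instruction to the subject is absolute. Section 6.1.3, at the Day 3 visit, provides enough cream for Days 4 to 27 and adds: "The subject will be instructed not to apply study drug on Day 28, Day 29, and Day 30". Section 5.6.1 names the same three days.

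Table 1 gives the Day 29 visit a window of plus or minus 3 days and places the restart visit at plus "2 days from Day 29". At that visit (Section 6.1.5): "The subject will be given sufficient study drug to enable once-daily application from Day 32 to the Day 56 exit visit".

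The compliance item in Section 5.6.11 is: "At each visit after Day 3 subjects will also be asked if they have applied the study drug every day in the morning". It makes no exception for the break. The same section says that any breach is to be entered in the eCRF.

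**The concern.** There are two gaps, both around the break.

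First, the rule moves with the session but the instruction does not. If the session is early in its window, a subject who follows the instruction exactly is still scheduled to apply cream inside the period that the rule wants free of it.

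Second, the compliance question treats a correctly skipped morning as a missed one, and nothing listed asks the opposite question of whether cream was withheld. The prohibited-product item does not reach it, because its wording is "Products containing oxymetazoline, except for study drug".

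Two things are at stake: a precaution that the protocol relies on to keep drug off the skin, and the attribution of adverse events to drug or device. Section 7.1.2.1 grades causality partly on the timing of the event relative to study drug administration, so the time of the last application is useful information at the second session and at the restart.

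**Working it through.** **Inputs.** Second session on day s, with s from 29 − 3 = 26 to 29 + 3 = 32 (Table 1), which is 7 permitted days. Named cream-free days are 28, 29 and 30 (Sections 5.6.1 and 6.1.3). Home supply is planned for Days 4 to 27 (Section 6.1.3). The restart is on site at s + 2 (Table 1, reading the window as anchored on the actual session). Dosing is in the morning (Section 5.6.1).

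**The plan's own figure.** For s = 29, the days s − 1, s and s + 1 are 28, 29 and 30: three cream-free days, as stated. Planned dosing days are 25 (Days 3–27) + 26 (Days 31–56) = 51, and 51 + 3 = 54 calendar days from Day 3 to Day 56. The nominal schedule is consistent.

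**Moving the session.** For each s, list which of s − 1, s and s + 1 are not named as cream-free.

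| Session day s | Not named cream-free | Planned home supply on those days? | Reading |
|---|---|---|---|
| 26 | 25, 26, 27 | Yes | Session day and day after are dosing days; Day 25 depends on clock time |
| 27 | 26, 27 | Yes | Session day is a dosing day; Day 26 depends on clock time |
| 28 | 27 | Yes | Depends on clock time only |
| 29 | none | – | Fits |
| 30 | 31 | No (ends Day 27) | Next planned dose on site, Day 32 |
| 31 | 31, 32 | No | Next planned dose on site, Day 33 |
| 32 | 31, 32, 33 | No | Next planned dose on site, Day 34 |

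**Clock time for s = 28.** The gap from the Day 27 dose to the session is 24 hours + (session time − dose time). With a dose at 08:00 and a session at 10:00 the gap is 24 + 2 = 26 hours, and the rule is met. With the times reversed it is 24 − 2 = 22 hours, and it is not. These times are illustrations; the documents give none. The firm conflicts are therefore s = 26 and s = 27, which is 2 of 7 permitted days, with s = 28 conditional. These are counts of permitted days, not of subjects. The documents do not say how sessions will be spread over the window.

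**The compliance question.** Assume a look-back to the previous visit. Section 5.6.11 states that look-back for its other items but not for this one. Count home mornings on the nominal schedule, leaving out on-site doses.

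| Check | Home mornings | Scheduled | Cream-free | Literal answer of a compliant subject |
|---|---|---|---|---|
| Day 29 | Days 4–28 = 25 | 24 | 1 | No |
| Day 31 | Days 29–30 = 2 | 0 | 2 | No |
| Day 56 | Days 32–55 = 24 | 24 | 0 | Yes |

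At 2 of the 3 checks the literal answer runs against compliance: a subject who ignored the break would answer yes.

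**Other places that might show the break was kept.** Section 5.6.12 asks about missed applications, not extra ones. The Day 29 and Day 31 procedure lists (Sections 6.1.4 and 6.1.5) have no last-application check. The dispensing log (Section 10.1) holds amounts, not days. SAP Section 6.1 summarises the number of days on which cream was applied, and a total does not show which days.

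**The case against.** The strongest reply is that no site would apply these sentences so literally. Staff know the regimen, so they will usually take the compliance item to mean scheduled days. Cream use during the break is a breach, and Section 5.6.11 requires any breach to be recorded. Section 8.3 already lists significant departures from the dosing schedule as major deviations. SAP Section 6.1 plans a count of application days and a listing of all treatment data, which suggests that dosing is captured in more detail than one yes/no answer. A site that books an early session can also re-instruct the subject. Section 5.6.1 has visit-day doses applied on site, and Table 1 lists no dose at the Day 29 visit, so a subject who follows that rule would not dose at home on the session day. Finally, Section 4.5 calls the separation an additional precaution and cites same-day use of a drug of the same class with energy therapy without reported safety concerns. Sections 5.6.1 and 5.6.7 let the investigator delay or stop cream.

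Most of this stands and keeps the point small. The recording rules cover use that comes to light, but none of them is a named question that would bring it to light. The visit-day rule does not help on Day 27 after a Day 26 session, and it sits beside a Day 3 instruction that points the other way.

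A reader might infer four stronger things that the documents do not support:

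- **That the break goes unchecked in practice.** The eCRF and the Study Manual are not among the documents, and either may hold a last-application item.
- **That 3 of the 7 permitted days breach the 24-hour rule.** Day 28 depends on clock times.
- **That late sessions are unprotected.** The named days do not cover them fully, but the planned supply ends at Day 27 and dosing restarts on site.
- **That compliant subjects would be lost from the main analysis.** Compliance does not enter the safety population (SAP Section 2.1). It bears on the per-protocol repeat of exploratory efficacy, which Sections 11 and 13 of the SAP trigger only if more than 20% of evaluable subjects have major violations.

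**Conclusion.** The point holds as a minor and cheap improvement. Followed as written, the fixed-day instruction conflicts with the washout rule for a session on Day 26 or 27, and possibly for one on Day 28. Read literally, the compliance question gives the wrong signal at Days 29 and 31. Neither document contains an item that directly asks whether cream was withheld.

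This rests on three assumptions: the plus or minus 3 day window applies to the session itself, the restart visit is anchored on the actual session date, and the compliance question looks back to the previous visit. The conclusion concerns what the protocol and SAP specify, not what sites will do. The safety population, the primary analysis and the sample size do not change.

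**What to change.** - **Instruction (Section 6.1.3, with the matching text in 5.6.1).** Tell subjects to use no cream from 24 hours before the second session until the on-site restart two days after it, whatever the day numbers.
- **Compliance item (Section 5.6.11).** Ask on how many scheduled dosing days since the last visit cream was not applied. Judge inadequate compliance in SAP Section 13 against scheduled days only.
- **Direct check.** Before the second session, record the date and time of the last application. Before the restart dose, record any cream use during the break, and enter such use as a schedule deviation.

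The cost is two or three eCRF fields and two reworded sentences, with no extra visit or staff. If the eCRF already records the last application and use during the break, only the wording changes are needed. How to manage a subject found to have used cream remains a clinical decision.
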